# APPENDIX I: ANTICIPATED ADVERSE EVENTS

Associated with Surgery and General Anesthesia	Simple/Radical Laparoscopic Nephrectomy or Laparoscopic Nephroureterectomy Surgery Specific
Acute Lung Injury	Air/Gas Embolism
Acute Respiratory Distress Syndrome	Chylothorax
Adhesions	Diaphragmatic Injury
Altered Mental Status	Emphysema
Anaphylaxis	Esophageal Injury
Anemia	Incisional hernia
Angina	Injury to other organs
Atelectasis	Intercostal nerve injury
Bacteremia	Internal Hernia
Bleeding	Pneumothorax
Bradycardia	Small bowel obstruction
Cardiac Arrhythmia	Splenic injury
Central line infection	Thromboembolic Event
Cerebrovascular Accident / Stroke	Wound infection
Congestive Heart Failure	
Constipation	
Death	
Deep Venous Thrombosis	
Dehydration	
Dementia	
Diarrhea	
DIC, Coagulopathy	
Dizziness	
Dyspnea	
Electrolyte Imbalance	
Fever, Pyrexia	
Headache	
Hematoma	
Hematuria	
Hypertension	
Hypotension, shock	
Нурохіа	
lleus	
Infection/SSI/Abscess	
Jaundice	
Lethargy	
Leukocytosis	

CONFIDENTIAL

Liver Failure	
Mesenteric Infarct	
Mesenteric Ischemia	
Myocardial Infarction	
Nausea	
Obtundation, Depressed Level of Consciousness	
Oliguria	
Pain (increased/severe/chronic)	
Pneumonia	
Port Site Hernia	
Pulmonary Edema	
Pulmonary Embolism	
Renal Failure	
Respiratory Failure	
Respiratory Insufficiency	
Sepsis	
Somnolence	
Systemic Inflammatory Response Syndrome	
Tachycardia	
Thrombocytopenia	
Thromboembolic Event	
Thrombosis	
TIA	
Tightness of the chest, Angina	
Tinnitus	
Urinary Retention	
Urinary Tract Infection (UTI)	
Volume Depletion, Hypovolemia	
Vomiting	
Wheezing	
Wound Dehiscence

1.1 Study Objectives

The primary objective of the trial is to demonstrate that the frequency of hemostatic interventions/procedures required intra-operatively or post-operatively related to the transection of the renal artery (RA) and renal vein (RV) during laparoscopic nephrectomies and nephroureterectomies with the powered vascular stapler (PVS) is not increased when compared to the standard of care (SOC) stapling device.

1.2 Study Design

This was a prospective, randomized, controlled, multi-center, open-label study that planned to collect and compare data from the surgeon's current SOC stapler (for RA/RV transection) and PVS. Prospective subjects were informed about the nature of the research, given the informed consent document (ICD) to read, and if the subject understood the consent, were asked to provide written consent.

2 Treatment Assignment

Subjects were assigned to either the surgeon's current SOC stapler or PVS. The ECHELON FLEX™ PVS with Advanced Placement Tip is a sterile, single use instrument that simultaneously cuts and staples tissue. There are four staggered rows of staples, two on either side of the cut line. The ECHELON FLEX™ PVS with Advanced Placement Tip and reloads have a staple line that is approximately 35 mm long and a cut line that is approximately 30 mm long. The shaft can rotate freely in both directions and an articulation mechanism enables the distal portion of the shaft to pivot to facilitate lateral access to the operative site. The powered vascular stapler has been cleared for marketing by the FDA and is CE marked which allows for commercial distribution in the European Union. The device was used in accordance with its product labeling and Instructions for Use.

3 Randomization and Blinding Procedures

Subjects were randomized to either the surgeon's current SOC stapler or PVS in a 1:1 ratio. Randomization could have occurred at any time prior to surgery up to transection of the vessel(s). Sites were instructed to wait until as close as possible to the actual time of vessel transection so as to minimize randomized drops within the study.

Randomization was accomplished through utilization of envelopes at the study site. Randomization envelopes were created according to the “Work Instructions for the Creation of Randomization Envelopes”, document number WE001625, based on a randomization schedule generated by the Ethicon Biostatistics group. The randomization schedule was generated using a validated program that incorporated variable block sizes, and treatment assignment was balanced within each study site. This was an open-label study and therefore no blinding procedures were required.

4 Interval Windows

Interval windows are not defined for the purpose of analysis in this study as the collection of data for the primary performance endpoint occurred intra-operatively and the collection of data for the primary safety endpoint occurred through hospital discharge and subsequent follow-up at the final visit. The final visit occurred approximately 4 weeks after surgery, thus no interval windows need to be defined given the absence of long-term follow-up in this study. The study protocol specified a window of 5 days around the scheduling of the 4-week follow-up visit, and any information entered in the eCRFs at this visit will correspond to the 4-week visit. There will be no assigning of observations to time points outside of the visit to which they are recorded in the eCRFs. The complete Schedule of Events for this study can be found in the Synopsis of the study protocol.

5 Primary and Secondary Endpoints

5.1 Primary Performance Endpoint

The primary performance (effectiveness) endpoint in this study was defined as the occurrence of hemostatic interventions/procedures completed for intra-operative bleeding related to the transection of the RA and RV with the use of either the SOC or PVS stapler. Hemostasis interventions or procedures were defined as bleeding detected and controlled intra-operatively (additional stapling, over-sewing, clip placement, compression, use of suture, sealant, and/or buttress, and/or use of energy); or bleeding that occurred intra-operatively requiring blood or blood product transfusion or an additional surgical procedure (e.g. conversion to open). No hemostasis intervention was defined as no bleeding at the staple line or bleeding that stopped after initial blotting of the staple line.

5.2 Primary Safety Endpoint

The primary safety endpoint was defined as the occurrence of hemostatic interventions/procedures completed for post-operative bleeding related to the transection of the RA and RV with the use of SOC or PVS. Hemostasis intervention was defined as bleeding that occurred post-operatively requiring blood or blood product transfusion or an additional surgical procedure (related to RA and RV transection). No hemostasis intervention was defined as no interventions needed for post-operative bleeding (related to RA and RV transection). This endpoint was recorded at the subject level as it was based on post-operative interventions and not specific to any individual firing.

5.3 Secondary and Additional Endpoints

Key additional endpoints in this study include: Surgeon Task Load Index, adverse events, and device usability questionnaires.

6 Levels of Significance

Evaluation of the acceptance criterion for this study is being accomplished through estimation of a 95% confidence interval. No hypotheses are specified for this study and no p-values are being calculated, therefore no level of significance is specified. All estimation of additional endpoints will be performed using 95% confidence intervals.

7 Analysis Sets

There will be three analysis sets defined:

- The Full Analysis Set (FAS) will consist of all randomized subjects who had a procedure performed and provide data on the number of surgical interventions.
- The Per Protocol (PP) Analysis Set will consist of all subjects in the FAS who had no major protocol violations. Determination of major deviations are conducted by the study Medical Director, Clinical Operations Trial Leader, Franchise Clinical Study Lead, and Biostatistician. A major deviation is defined as: A departure from the study protocol that has the potential to affect the scientific validity of the study (including deviations that: a) impact the analysis of the primary endpoint, or b) are due to inappropriate enrollment of a subject that does not meet the inclusion/exclusion criteria) or the safety, rights and welfare of the enrolled subject.
- The Safety Analysis Set consists of all randomized subjects on whom a procedure is started.

The primary performance endpoint analysis will be performed on the Full Analysis Set and subjects will be classified according to their randomized treatment group. The primary performance endpoint analysis will also be performed on the PP set as a sensitivity analysis to the results on the FAS. The analysis of additional endpoints will also be performed on the Full Analysis Set. Analysis of the primary safety endpoint and adverse events summaries will be performed on the Safety Analysis Set.

8 Sample Size Justification

Approximately 250 subjects were planned to be randomized in the study in a 1:1 ratio to SOC or PVS. Historical clinical study data on a similar powered surgical stapler demonstrated a need for staple line interventions in approximately 6% of firings on the pulmonary artery or pulmonary vein. This data also showed an average of 2.6 to 2.9 firings per subject, and it is expected, given differences in device design and procedure, that each subject would have required 2 to 3 firings on the renal vein or renal artery in the current study.

Given that it was expected to have a minimum of 300 firings in each group, the sample size of approximately 250 subjects total was considered adequate for descriptive summarization of the primary performance endpoint, i.e. number and frequency of intra-operative surgical interventions. Assuming an approximate background intervention rate of 6%, the given sample size was to have provided reasonable precision in the estimation of the intervention rate to an expected margin of error for a 95% confidence interval of at most 2.9% for each group.

During development of the protocol with the Notified Body (TUV) following their decision to grant CE mark to the device, a formal hypothesis was not defined for the study; however, to establish that the hemostasis intervention rate of PVS is not increased compared to SOC, an acceptance criterion was developed and a 95% confidence interval for the difference in the proportion of firings requiring interventions for PVS minus SOC will be calculated. The powered vascular stapler will be considered to have acceptable performance if the upper bound of the 95% confidence interval does not exceed 3%.

While the given sample sizes were expected to provide reasonable precision for estimation of the hemostasis intervention rate within each treatment group, the study was not sufficiently powered for demonstrating that the between treatment group comparison could achieve the 3% acceptance criterion. The given sample sizes are not large enough to control expected variability of the difference in rates between groups with a high probability, even if the true intervention rates are equivalent, thus increasing the likelihood of not meeting this acceptance criterion.

Given the increased risk of not meeting the acceptance criterion due to an undersized study, additional analyses are being prospectively planned to help provide additional information on the types and severity of interventions that may be needed in each treatment group. These are detailed in Section 10.4.1 below.

9 Data Monitoring Committee (DMC)

No Data Monitoring Committee was planned or utilized during this study.

10 Analyses to be Conducted

10.1 General Conventions

Subject data will be summarized using listings and tables. All eCRF data will be listed per subject for all subjects. Descriptive statistical analyses will be provided for pre-specified study endpoints. Summaries for continuous variables will include number of observations (n), mean, standard deviation, median, minimum, and maximum. Summaries for categorical variables will include number and percentage.

Analyses will be conducted using SAS software version 9.4 or higher. During the course of analysis programming of tables that are mocked up in this SAP, minor modifications may become necessary.

Examples of these minor modifications include, but are not limited to, re-wording of a footnote, addition of a footnote, re-labeling of a column, or addition or removal of a column from a listing. In cases where modifications to tables or listings are not related to a change in statistical analysis methodology or conclusions that could be made on the originally proposed methodology, then no amendment of the SAP is necessary. Amendment of the SAP is required in any case where changes to statistical analyses that were planned in the original signed SAP are proposed.

10.2 Disposition of Study Subjects

Subject disposition will be summarized by randomized treatment group and overall using counts and percentages. The number and percentage of subjects in each analysis set will be tabulated. Additionally, the number and percentage of subjects completed and discontinued will be tabulated along with the specific reasons for discontinuation.

10.3 Demographic, Baseline, and Surgical Characteristics

Summary statistics of subject demographics (age, gender, race, and ethnicity) will be presented by randomized treatment group and overall for the Full Analysis Set. Surgical characteristics including, at minimum, type of surgery (nephrectomy or nephroureterectomy), number of ports used, number of renal arteries transected, number of drains placed, ASA physical status, estimated blood loss, conversion to open, requirement for blood transfusion, procedure duration, and drain duration will be summarized by randomized treatment group and overall. Results of tumor assessments performed by the pathology laboratory (including tumor stage, maximum tumor diameter, and maximum tumor depth) will also be summarized by randomized treatment group and overall.

10.4 Primary Endpoint Analyses

For the primary performance endpoint, summary statistics and 95% confidence intervals will be provided for the number and frequency of interventions by randomized treatment group. An intervention is defined as any firing which required a hemostasis intervention.

To account for the potential dependence among firings within a subject, the 95% confidence interval within each treatment group will be estimated using a bootstrap approach. For each subject, the outcome of each firing will be represented by a vector of 0's (indicating no intervention needed) and 1's (indicating an intervention was needed). This vector will be re-sampled with replacement to generate a bootstrap sampled vector of observations for each subject. Then, the proportion of observations requiring intervention for each subject will be calculated from this bootstrap vector. After obtaining a sample proportion of firings requiring intervention for each subject, the mean of these sample proportions will be calculated across all subjects within that treatment group to provide an estimated sample proportion of firings requiring intervention based on 1 iteration of the bootstrap process. This process will then be repeated a minimum of 5000 times to generate a sampling distribution for the proportion of firings requiring intervention within each treatment group. The mean of this sampling distribution will be provided as the point estimate of the

proportion of firings requiring intervention for that treatment group and the 95% confidence interval will be estimated by the lower 0.025 and upper 0.975 percentiles of this sampling distribution.

The table below demonstrates 1 iteration of this bootstrap process within a treatment group.

Subject ID	Observed Data Vector	Bootstrap Sampled Vector	Bootstrap-Based Sample Proportion
1	(0, 0, 1, 0, 0)	(0, 1, 0, 1, 0)	0.40
2	(0, 0, 0)	(0, 0, 0)	0.0
3	(0, 1, 0, 0)	(1, 0, 0, 0)	0.25
4	(0, 0, 1, 0, 0)	(0, 0, 0, 0, 0)	0.0
5	(0, 0)	(0, 0)	0.0
...
...
125	(1, 0, 0, 1, 0)	(0, 1, 0, 0, 0)	0.20
Summary			Average of above proportions to get 1 observation in the sampling distribution of the proportion of firings requiring intervention.

The above re-sampling process will then be repeated a minimum of 5000 times to estimate the sampling distribution for each treatment group.

For each of the 5000 iterations, the difference in bootstrap estimated sample proportions (PVS – SOC) will be calculated and these values will be used to estimate the sampling distribution of the difference between PVS and SOC in the proportion of firings requiring intervention. The mean of this sampling distribution will be provided as the point estimate for the difference of the proportion of firings requiring intervention between groups and the one-sided upper-tailed 95% confidence interval limit for the difference will be estimated by the upper 0.95 percentile of this sampling distribution.

A secondary estimate of the proportion of firings requiring intervention will be provided under the assumption of independence of firings within a subject. This will be performed based on the total number of firings and the percentage will be calculated as the number of firings requiring an intervention divided by the total number of firings. The following SAS code will be used to generate two-sided 95% confidence intervals for the individual treatment groups and a one-sided upper-tailed 95% confidence interval for the difference between groups:

```
proc sort data=hemo_interv;
  by TrtGroup descending event;
run;
```

```

*two-sided exact 95% confidence interval for within treatment summary;
proc freq data=hemo_interv order=data;
  tables TrtGroup*event/binomial riskdiff exact;
run;
*one-sided exact 95% confidence interval for between treatment summary;
proc freq data=hemo_interv order=data;
  tables TrtGroup*event/binomial riskdiff alpha=0.10;
  exact riskdiff;
run;

```

This code assumes that the dataset hemo_interv contains one record per firing, the variable ‘TrtGroup’ contains the identifier for randomized treatment group (the SOC group should be listed in the first row of the table), and the variable ‘event’ identifies an occurrence of the primary endpoint with a 1 and no occurrence of the primary endpoint with a 0. The resulting output in the Column 1 Risk Estimates table in the SAS Output Window provides the individual confidence intervals for each treatment group as well as the confidence interval for the difference between groups. The above approach utilizes the exact methodology of Clopper and Pearson for estimation of the confidence intervals within each group as well as the difference between groups.

Additional summaries will be provided to tabulate the total number of vessels transected as well as the specific type of vessel that was transected – renal artery or renal vein. The specific types of interventions that were performed will also be tabulated by randomized treatment group.

The primary safety endpoint, the occurrence of hemostatic interventions/procedures completed for post-operative bleeding related to the transection of the RA and RV, is measured at the subject level and will be analyzed using the same methodology as described above for independent observations. A similar dataset will be created that contains one record per subject and an indicator for whether or not the subject experienced a post-operative intervention event. The SAS code provided above will be utilized in a similar manner for this analysis.

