# 7.4 ANALYSIS OF EFFECTIVENESS

Summary statistics and 95% confidence intervals will be provided for the number and frequency of interventions for the set of SOC subjects and PVS subjects separately. This will be performed based on the total number of firings. An intervention is defined as any firing which is classified as hemostasis intervention. To establish that the intervention rate is not increased compared to SOC, a 95% confidence interval for the difference in proportion of firings requiring interventions for PVS minus SOC will be calculated and powered vascular stapler will be considered to have acceptable performance if the upper bound of the 95% confidence interval does not exceed 3%.

Additional endpoints will be summarized with descriptive statistics and 95% confidence intervals as appropriate for continuous or categorical measurements.

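### The primary bootstrap redraws firings within fixed subjects instead of resampling subjects, so the limit judged against 3% is too low and false acceptance runs at about two to four times nominal

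*SAP*

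**What the plan says.** SAP 10.4 (Primary Endpoint Analyses) gives the purpose of the method: "To account for the potential dependence among firings within a subject, the 95% confidence interval within each treatment group will be estimated" by a bootstrap. Each subject is represented by a vector with one 0 or 1 per firing, and the resampling step is "This vector will be re-sampled with replacement to generate a bootstrap sampled vector of observations for each subject". Each subject's proportion is computed from the redrawn vector, and "the mean of these sample proportions will be calculated across all subjects within that treatment group". This is done at least 5000 times.

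The worked table in the same section confirms the reading. Subjects 1 to 125 each appear exactly once, and every row is redrawn only from its own data. Subjects 2 and 5, whose firings are all zero, can only return zero.

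For the comparison, the PVS minus SOC difference is taken at each iteration and "these values will be used to estimate the sampling distribution of the difference between PVS and SOC in the proportion of firings requiring intervention". Then "the one-sided upper-tailed 95% confidence interval limit for the difference will be estimated by the upper 0.95 percentile of this sampling distribution". The analysis that treats firings as independent is labelled secondary, so the bootstrap limit is the primary one. Under SAP Section 8 (Sample Size Justification), PVS has "acceptable performance if the upper bound of the 95% confidence interval does not exceed 3" percent. Protocol 7.4 has the same criterion and says only that "a 95% confidence interval for the difference in proportion of firings requiring interventions for PVS minus SOC will be calculated", without stating whether the interval is one-sided or two-sided.

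**The concern.** Firings within a subject may be correlated, and subjects are the units that were randomised. A bootstrap that allows for this must let the set of subjects vary between iterations. The SAP holds that set fixed and varies only the firings inside each subject, so the between-subject variation that within-subject dependence creates never enters the interval. A subject with identical outcomes at every firing, or with a single firing, adds no variance at all.

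At a 6% rate this describes most subjects. With 2 independent firings the chance of a mixed outcome is 2 × 0.06 × 0.94 = 11.3%. About 14 of 125 subjects would then carry the whole bootstrap variance.

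The limit affected is the one that decides whether PVS performs acceptably. If it is too low, a device that is 3 points worse passes too often. The within-arm intervals would also be reported as 95% intervals when they are not.

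**Working it through.** **Inputs from the documents** (SAP Section 8; Protocol 7.2 and 7.4): about 250 subjects at 1:1, so 125 per arm; 2 to 3 firings per subject; at least 300 firings per arm, which is 300/125 = 2.4 per subject; background rate 6%; margin 3 points; 0.95 percentile as the limit (SAP 10.4), hence a nominal one-sided error of 5%. The documents do not quote that error rate; it follows from the limit. At the margin the true rates are SOC 6% and PVS 9%.

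**Assumption:** the documents give no within-subject correlation *r*, so 0 to 0.3 is used.

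**The plan's own precision figure.** For 18 events in 300 firings, the half-width of a 95% interval is 1.96 × √(0.06 × 0.94/300) = 2.69% (Wald) and 2.86% (Clopper-Pearson). The stated maximum of 2.9% is reproduced, so the inputs are read correctly.

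**Variance of the SAP bootstrap.** With *m* firings per subject and rate *p*:

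- True variance of an arm's mean proportion: p(1−p)[1+(m−1)r]/(mN).
- Bootstrap variance: (1/N²) Σ p̂ᵢ(1−p̂ᵢ)/m. Its expectation is p(1−p)(1−r)(m−1)/(m²N).
- Ratio, bootstrap to true: (1−r)(m−1)/m ÷ [1+(m−1)r].
- Approximate false acceptance at the margin: Φ(−1.645 × √ratio).

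Worked case, m = 2 and r = 0: ratio = 1/2, standard-error ratio = 0.707, and Φ(−1.163) = 12.2%.

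| Firings | r | SE ratio | False acceptance (nominal 5%) |
|---|---|---|---|
| 2 | 0 | 0.71 | 12.2% |
| 3 | 0 | 0.82 | 9.0% |
| 2 | 0.2 | 0.58 | 17.1% |
| 3 | 0.2 | 0.62 | 15.5% |
| 2 | 0.3 | 0.52 | 19.7% |
| 3 | 0.3 | 0.54 | 18.7% |

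The bootstrap variance carries the factor (1−r) and the true variance carries 1+(m−1)r. As dependence rises, the SAP interval narrows when it should widen.

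**Simulation.** Beta-binomial firings, 125 subjects per arm, a mix of 2 and 3 firings with mean 2.4, 2000 to 3000 trials per scenario, 800 to 1000 resamples each. The comparator resamples whole subjects. The standard errors and false acceptance are at 9% versus 6%. Coverage and the last column are at 6% in both arms.

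| r | SE of difference, SAP / true (points) | False acceptance, SAP / whole-subject | Within-arm 95% coverage, SAP / whole-subject | Acceptance at equal rates, SAP / whole-subject |
|---|---|---|---|---|
| 0 | 1.6 / 2.2 | 11–12% / 5–6% | 84–85% / 94–95% | 62% / 47% |
| 0.1 | 1.5 / 2.3 | 14.1% / 5.6% | 80% / 93% | 63% / 44% |
| 0.2 | 1.5 / 2.5 | 18.3% / 6.3% | 76% / 95% | 64% / 40% |
| 0.3 | 1.4 / 2.6 | 20.8% / 5.8% | 69% / 94% | 67% / 39% |

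With exactly 2 firings, false acceptance under the SAP method is 13.1% at r = 0 and 20.5% at r = 0.3. With exactly 3 it is 10.5% and 18.4%. If some subjects have a single firing it is worse: an assumed 1-to-4 firing mix with mean 2.4 gives 15.8% and 21.7%.

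The last column shows the reversal. At equal rates, more dependence raises acceptance under the SAP method (62% to 67%), while under whole-subject resampling it falls (47% to 39%).

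If the protocol's interval is read as two-sided (0.975 percentile, nominal 2.5%), the SAP method gives 6.4% to 17.5% over these scenarios.

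**The case against.** - **The upper end rests on an assumed correlation.** This stands. The factor of four needs *r* near 0.3, which no document gives. The factor of about two needs no correlation. For exactly 3 independent firings it is 1.8 analytically (9.0%) and 2.1 by simulation (10.5%). More firings would shrink the error further (7.1% at 5 independent firings), but the plan expects 2 to 3.
- **No hypothesis or significance level is specified** (SAP Section 6). True, but a pass/fail rule applied to a one-sided 95% limit implies a 5% error at the margin, and the within-arm intervals are wrong regardless of any hypothesis.
- **The SAP already concedes low power for the 3% criterion.** That concession is about failing an equivalent device. The error here is passing a worse one, so the two do not offset each other.
- **The independent-firings interval appears beside the bootstrap in Table 6.** This is a partial safeguard. A pooled Wald limit, used as a stand-in for the SAP's exact limit, gave 5.8%, 6.3% and 9.8% false acceptance at r = 0, 0.1 and 0.3. However, it is secondary, it ignores clustering, and the SAP has no rule for when the two limits disagree.
- **The interval could be meant as conditional on the enrolled subjects.** The SAP does not say so, and this reading would not rescue the method. Conditional on each subject's own probability, the bootstrap variance is still only (m−1)/m of the correct one: half at 2 firings and two-thirds at 3.

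**Conclusion.** The concern holds. The text and the worked table are unambiguous, and no other section adds a step that resamples subjects. The primary limit is built on a standard error that is 18% to 29% too small with independent firings, and 46% to 48% too small at a correlation of 0.3. False acceptance at the 3-point margin is about twice the nominal 5% without any correlation and about four times at *r* = 0.3. This assumes 125 subjects per arm, 2 to 3 firings each, and rates of 6% and 9%. The error favours the investigational device, and the method works against the purpose the SAP gives for it. It should be corrected before the primary analysis is run.

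**What to change.** Replace the resampling step in SAP 10.4. In each iteration, draw subjects with replacement within each arm, keep every drawn subject's firing vector unchanged, compute the arm estimate, take PVS minus SOC, and use percentiles of those differences. Redraw the worked table so that subject identifiers, not firings, are resampled.

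State the arm estimate explicitly, since it is a separate choice. Interventions divided by firings over the drawn subjects fits the per-firing basis in Protocol 7.4. The SAP's mean of subject proportions can be kept without spoiling the correction: with whole subjects resampled it gave 5.9% to 6.3% false acceptance in a separate simulation. A GEE or ratio estimate with a subject-clustered robust standard error is an alternative, but its weighting of subjects must be stated. Also state that this limit is the one compared with 3%.

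The cost is a SAP amendment, which SAP 10.1 requires for a change to a planned analysis, and a few lines of code. No new data are needed. The interval widens and the criterion becomes harder to meet. At equal 6% rates and independent firings, acceptance falls from about 61% to 43% with 2 firings per subject, 62% to 47% with a mean of 2.4, and 66% to 56% with 3. The percentile limit from whole-subject resampling stays slightly liberal in simulation (5.0% to 6.3%).
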